Medication adherence	Know your medications and which ones you take. Have a written list and bring to each health care visit.	Feedback to PCP, nurse case manager Offer medication organizer	Self-reported medication adherence (Voils, C. I. et al.)  ReCOMP 
Communication with medical team/physician	Be involved with your health care. There are many ways to take an active role.	Feedback to PCP, nurse case manager for appropriate follow up	CAHPS-provider communication 
Optional Education modules- if applicable to individual Veteran			

Weight reduction, maintenance of normal BMI	Strive for a healthy weight. If you need to lose weight, even a small amount can improve your health. If you are a normal weight, maintain it.	Referral to MOVE program, assistance with enrollment questionnaire (MOVE23)	BMI
Smoking cessation	Be tobacco free! If you are using tobacco, ask your health care team for help in quitting.	Referral to smoking cessation resources, provide quit line number	Self-report of smoking status New medication for smoking cessation
Limiting alcohol intake	If you choose to drink, do so in moderation. If drinking, limit to <= 2 drinks/day for men, <= 1 drink for women	Feedback to PCP, nurse case manager for appropriate follow up	AUDIT-C 
Stress management, depression and sleep	Pay attention to stress. Tools are available to help you manage and reduce stress.	Feedback to PCP, nurse case manager for appropriate follow up; Referral to Mindfulness based stress reduction class	PHQ-8 

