#### b) Self-management behaviors and patient-provider communication

Self-management behaviors will be measured with the following scales: The nutritional assessment of eating behavior will be a self-reported assessment "Starting the conversation", an eight-item validated, simplified food instrument designed for use in primary care and health-promotion settings. We will utilize a food frequency questionnaire (FFQ) developed by the Nutrition Assessment Shared Resource of the Fred Hutchinson Cancer Research Center to measure nutritional intake. The FFQ provides estimates for 30 nutrients and has acceptable accuracy and reliability. Intake of fruits and vegetables, fat, and fiber can be calculated based on published algorithms. Level of physical activity will be assessed using the International Physical Activity Questionnaire (IPAQ), a validated and reliable measure of physical activity. All participants will have an assessment of medication adherence using a standardized participant interview. In addition, yearly medication adherence will be calculated from the electronic pharmacy data (ReComp). Tobacco use will be assessed with standard questions from the Behavioral Risk Factor Surveillance Survey (BRFSS). *We will assess alcohol consumption using the Alcohol Use Disorders Identification Test (AUDIT-C), a 3-item screening test for heavy drinking and/or abuse. We will ask about utilization of stress management techniques and patient-provider communication using previously validated questionnaires (CAHPS ).*

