**Table 4. Outcome Measures; measured at baseline and 12 months**

	Measurement domain	Measurement instrument
Primary outcome		
Blood pressure	Systolic blood pressure (SBP)	Standard protocols 
Secondary outcomes		
Cardiovascular risk	Framingham risk score (FRS)	FRS algorithms 
Individual Cardio-metabolic risks	Body Mass Index (BMI) Low density lipoprotein cholesterol (LDL-c)	Standard protocols for height and weight Laboratory data from CPRS if within 3 months of enrollment, otherwise drawn by study RN at enrollment

Health Care Utilization	Outpatient and ER visits, hospitalizations, pharmacy utilization	Administrative data and participant self-report for non-VA care
Health-related quality of life	Role limitations caused by physical health, emotional problems, physical functioning, and general health	SF-12 
Intermediate outcomes		
Patient activation, Self-efficacy	Self-rated ability to take preventive actions, manage symptoms of medical problems, find and use appropriate medical care, and work with their health care providers	Patient Activation Measure (PAM) 
Social Support	Domains of Social support	Multidimensional Scale of Perceived Social Support 
Self-management Behaviors – Measure of behavioral enactment	Physical activity Nutrition – eating behavior, food frequency Medication adherence  Tobacco use Alcohol use Stress Management	IPAQ  “Starting the conversation”  , FFQ  Voils, C. I. et al. Medication adherence questionnaire  ReCOMP  Medication Possession Ratio BRFSS  AUDIT-C  Utilization of stress management techniques 
Patient provider communication	Communication with physician and health care team	Consumer Assessment of Health Plans (CAHPS)-patient-provider communication 

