5. STUDY OUTCOMES

Primary outcome:

Primary outcome -- continuous change in systolic blood pressure. At baseline and exit (12 months); 3 blood pressure readings were obtained using standard procedures. The average of the 3 blood pressure measurements is used. Blood pressure was assessed at a baseline enrollment visit using standardized protocols, measured by a trained research assistant, using an A&D Medical Ua-767f Multi-User Blood Pressure Monitor blood pressure cuff. Measurements were taken three times. If participant failed to schedule an exit visit, blood pressures were extracted from the medical record for a 3-month period around the date of the exit visit. The lowest value will be used from the CDW for that day.

Secondary outcomes:

Secondary outcome — SBP control. This is a dichotomous outcome in which control is defined as the percentage of respondents meeting pre-specified blood pressure goal (BP \leq 120/80) as based on current VHA/DOD/AHA guidelines.

BP Category	SBP		DBP
Normal	<120 mm Hg	and	<80 mm Hg
Elevated	120–129 mm Hg	and	<80 mm Hg
Hypertension			
Stage 1	130–139 mm Hg	or	80–89 mm Hg
Stage 2	\geq 140 mm Hg	or	\geq 90 mm Hg

All outcomes were measured at baseline and at 12 months. Laboratory examination at both baseline and follow-up includes a non-fasting lipid panel (total, low density lipoprotein [LDL] and high-density lipoprotein [HDL] cholesterol; triglycerides) and are utilized to calculate one of the secondary outcomes, the Framingham Risk Score. Other secondary outcomes include health-related quality of life (HRQOL) measured with the SF-12 and health care utilization.

Intermediate outcomes:

Self-management behaviors were measured at baseline and 12-months that are intermediate outcomes, such as nutrition, physical activity and medication adherence. The nutritional assessment includes a self-reported assessment of dietary intake “Starting the conversation” an eight-item validated, simplified food frequency instrument designed for use in primary care and health-promotion settings. Level of physical activity at baseline and follow-up is assessed using the International Physical Activity Questionnaire (IPAQ), a validated and reliable measure of physical activity (PA) level that classifies participants as high (e.g. over 60 minutes of moderate-intensity PA per day), moderate (e.g. 30 minutes of at least moderate-intensity PA on most days), or low. Medication adherence is assessed using a standardized participant interview.

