Covariates:

Key covariates include those that have been shown in previous studies to be associated with hypertension control and self-care. Self-reported demographic covariates include age, gender, marital status, education, annual income and race/ethnicity. Self-reported race and ethnicity questions were taken from the Behavioral Risk Factor Surveillance System (BRFSS) Questionnaire. Race responses were then classified as American Indian or Alaskan Native, Asian Indian, Chinese, Filipino, Japanese, Korean, Vietnamese, Native Hawaiian, Guamanian or Chamorro, Samoan, Black or African-American, White or other. We ask them separately to define their ethnicity as Hispanic, Latino or Spanish origin. We include questions to measure health literacy in adults. We assess alcohol consumption using the Alcohol Use Disorders Identification Test (AUDIT-C), a 3-item screening test for heavy drinking and/or abuse. Because of the strong link between depression and poor self-care, depressive symptoms are assessed using the Patient Health Questionnaire-8 (PHQ-8). We also collect data on costs and utilization obtained from VHA administrative data.

Outcome Measures; measured at baseline and 12 months		
	Measurement domain	Measurement instrument
Primary outcome		
Blood pressure	Systolic blood pressure (SBP)	Standard protocols
Secondary outcomes		
Cardiovascular risk	Framingham risk score (FRS)	FRS algorithms
Individual Cardio-metabolic risks	Body Mass Index (BMI)	Standard protocols for height and weight
	Low density lipoprotein cholesterol (LDL-c)	Laboratory data from CPRS if within 12 months of enrollment, otherwise drawn at enrollment, and within 3 months of the exit visit
	Tobacco use	Self-report from BRFSS questions
Health Care Utilization	Outpatient (including specialty care visits) and ER visits, hospitalizations utilization.	Self-report and VA administrative data
Health-related quality of life	Role limitations caused by physical health, emotional problems, physical functioning, and general health	SF-12

Outcome Measures; measured at baseline and 12 months		
Intermediate outcomes		
Patient activation, Self-efficacy	Self-rated ability to take preventive actions, manage symptoms of medical problems, find and use appropriate medical care, and work with their health care providers	Consumer Health Activation Index (CHAI)

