Social Support	Domains of Social support	8-item Medical Outcomes Study (MOS) Social Support Survey Instrument & Behavioral Risk Factor Surveillance System (BRFSS) Questionnaire
Self-management Behaviors – Measure of behavioral enactment	Physical activity Nutrition – eating behavior, food frequency Medication adherence Alcohol use Stress Management	IPAQ “Starting the conversation,” FFQ Voils et al Medication BRFSS AUDIT-C
Patient provider communication	Communication with physician and health care team	Consumer assessment of health plans (CAHPS)-patient provider communication

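### The SAP omits the protocol's pharmacy-refill adherence measure (ReComp), so the Aim 2 adherence comparison has no objective check on self-report

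*SAP*

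**What the plan says.** Protocol section 5.5, under self-management behaviors, gives two adherence measures. The first is self-report: "All participants will have an assessment of medication adherence using a standardized participant interview". The second follows directly: "In addition, yearly medication adherence will be calculated from the electronic pharmacy data (ReComp"). The refill measure also appears in Table 2 (section 5.1), against the medication adherence module, and in Table 4 (section 5.5), which adds "Medication Possession Ratio".

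The SAP, section 5, Intermediate outcomes, has one sentence on the subject: "Medication adherence is assessed using a standardized participant interview". Its outcome table keeps adherence as a domain ("food frequency Medication adherence Alcohol use Stress Management") but shows no refill instrument. Neither ReComp nor a possession ratio appears anywhere in the SAP. Administrative data are mentioned for other purposes: "We also collect data on costs and utilization obtained from VHA administrative data". No reason for the omission is given.

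SAP section 6 still compares every Aim 2 intermediate outcome between arms, using the primary-outcome model or its logit version.

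**The concern.** Protocol section 5.1 acknowledges that assignment cannot be blinded. Medication adherence is one of five required coaching modules, and the key message in Table 2 is "Know your medications and which ones you take. Have a written list and bring to each health care visit". Intervention Veterans are scheduled for ten calls over the year and receive a pill organiser. At follow-up calls, pillboxes are offered where adherence problems are noted. A Veteran coached repeatedly on a behaviour, who knows why, may describe that behaviour more favourably at exit whether or not it changed.

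The refill measure guards against this because it does not depend on what the participant says. Without it, a between-arm difference in reported adherence could reflect better medication-taking, more favourable answering, or both, and the analysis could not separate them. Adherence is a named Aim 2 target, and the protocol's introduction calls it critical in hypertension, so the result will be used to explain any blood pressure effect.

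A second loss concerns missing data. The interview needs the exit contact, for which the protocol plans 15% attrition. A refill measure needs no contact.

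**Working it through.** **Text comparison.** The documents state no figure for adherence, so the main check is to set the entries side by side.

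| Place | Self-report | Refill measure |
|---|---|---|
| Protocol Table 2 | yes | ReComp |
| Protocol 5.5, text | yes | ReComp, yearly, in addition |
| Protocol Table 4 | yes | ReComp and possession ratio |
| SAP 5, text | yes | none |
| SAP 5, outcome table | yes (entry looks cut short) | none visible |
| SAP 6 | no instrument named | none |

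The adherence entry in the SAP table breaks off mid-phrase, so I give that cell no weight. The SAP text sentence is intact. It restates the protocol's interview sentence and has nothing corresponding to the refill sentence that follows it there. The SAP also changes other instruments: the Consumer Health Activation Index replaces the Patient Activation Measure, and the MOS social support survey with BRFSS items replaces the Multidimensional Scale. The SAP list is therefore a revised one, not just a shortened copy.

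**Illustration of what is at stake.** Assume no true adherence effect and a pure reporting shift of d standard deviations in favour of the intervention. The documents give no value for d; 0.1 to 0.3 is an assumed range. The two-sided alpha of 0.05 is the level the SAP sets for the primary hypothesis.

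- Number per arm: 200 randomised less 15% is 200 × 0.85 = 170. The protocol's sample size section states 177. Both are shown.
- SE of the standardised difference = √(2/n). For n = 170 this is √(2/170) = 0.108.
- Chance of a significant result = Φ(d/SE − 1.96) + Φ(−d/SE − 1.96).
- Design effect from the protocol's ICCs and cluster sizes: 1 + (5 − 1) × 0.015 + (35 − 1) × 0.007 = 1 + 0.060 + 0.238 = 1.298. Effective n = 177/1.298 = 136, or 170/1.298 = 131.

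| Assumed shift | n = 170, unclustered | n = 177, unclustered | n = 170, design effect 1.298 | n = 177, design effect 1.298 |
|---|---|---|---|---|
| 0.1 SD | 15% | 16% | 13% | 13% |
| 0.2 SD | 45% | 47% | 37% | 38% |
| 0.3 SD | 79% | 81% | 68% | 70% |

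The nominal rate is 5%. The clustered columns borrow ICCs planned for blood pressure and apply coach clustering to both arms, although the model has it in the intervention arm only.

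**The case against.** The strongest reply is that the SAP never says ReComp was withdrawn. The relevant table cell is damaged just where ReComp would follow, and the SAP text is illustrative: for nutrition it names one questionnaire, yet the table also lists the food frequency questionnaire. Silence in the text is not proof of removal, and the protocol still requires the measure. This stands against anyone who infers a deliberate withdrawal; the documents do not show one. It does not remove the conflict, because the SAP governs the analysis and as written specifies no refill outcome.

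A reader might also take the SAP's health care use row, "Outpatient (including specialty care visits) and ER visits, hospitalizations utilization", as confirmation, since Table 4 of the protocol lists pharmacy use there. It is weak evidence. The protocol's own text on utilization in section 5.5 and its Aim 1 also leave pharmacy out, so Table 4 is the outlier.

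It is also tempting to say that only one arm learns the desired answer. The protocol gives controls a pamphlet with the same information content, and outcome interviews are done by research staff, not coaches. What remains is that one arm is coached repeatedly and the other is not. That makes differential reporting plausible, not certain.

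Finally, refill data have limits. They record dispensing, not ingestion, and miss non-VA fills. The documents do not say what share of participants fill at VA, so a claim of near-complete coverage has no support. Because the intervention links Veterans to VA care, fills could move into VA in one arm, making capture differ by arm. This is a good reason not to let ReComp overrule self-report, but not a reason to leave it out.

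**Conclusion.** The protocol and SAP conflict on how adherence is measured. Followed as written, the SAP tests a coached behaviour in an unblinded trial on self-report alone. That part rests on the text and needs no assumption about numbers.

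The percentages above depend on assumed reporting shifts. A reader might take them as the trial's actual error rate for adherence; the documents give no bias size and do not support that. They show only that a modest differential, if present, would raise the false-positive risk well above 5% under each assumption tried.

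Nor does the point reach the primary result. Adherence is one of several intermediate outcomes, the main conclusions rest on systolic blood pressure, and the sample size and power are unaffected. The gap is worth closing because it limits what Aim 2 can say about mechanism.

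**What to change.** Restore ReComp to SAP section 5 as an intermediate adherence outcome beside the self-report questionnaire. Specify that it is:

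- computed identically in both arms from VA pharmacy data;
- measured over the 12 months after randomisation and adjusted for the pre-randomisation value;
- calculated for Veterans who miss the exit contact as well as those who complete it;
- defined as to the drug classes counted and the handling of non-VA fills.

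Report both measures and interpret them together, with no rule that either overrides the other. State as limitations that refills measure dispensing and that capture of non-VA fills may differ by arm. If the omission was intended, record the reason and label the self-report result as open to reporting bias. Either change should be dated before any between-arm adherence comparison is seen.

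The cost is a short SAP amendment and one pharmacy extract. The study already uses the Corporate Data Warehouse and a project programmer for recruitment, and administrative data for utilization. No new participant contact is needed, and the records can be drawn retrospectively.

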6. STATISTICAL ANALYSES AND DESCRIPTION OF MAIN TABLES

The primary outcomes are changes from baseline to one year in systolic blood pressure. We will test the primary hypothesis that among Veterans with poorly controlled hypertension and at least one other CVD risk, the **Vet-COACH** intervention targeting behavior change and disease self-management will decrease SBP by 4 mmHg compared to a usual care + education control group. Primary analyses will be conducted on an intent-to-treat basis; participants will be analyzed in the group to which they were assigned, regardless of intervention adherence, using all follow-up data or up to last available measurement prior to exclusion or dropout.

Primary Effectiveness Analyses for Specific Aims 1 & 2

Since there are multiple patients enrolled per physician and multiple patients enrolled per peer health coach, a physician-level and peer health coach random effect will be included in the primary analytic model to take this correlation into account. For the Aim 1 primary outcome analysis, we will evaluate change in systolic blood pressure, from baseline to 12 months, in the intervention versus controls using the following random effects model:

$$Y_{ij} = \mu + \beta_1 \text{Group}_{ij} + \beta_2 \text{Baseline}_{ij} + \beta_3 x_{ij} + \alpha_j + \text{Group}_{ij} * \tau_k + \epsilon_{ijk}$$

where Y_{ij} is the change in blood pressure from baseline to 12 months for subject i having provider j (and k for peer coach intervention participants); μ is the overall mean; Group_{ij} is group assignment (intervention vs. control); Baseline_{ij} is the baseline BP value; x_{ij} are baseline covariates that could affect the outcome; α_j is the random effect for provider cluster j and τ_k is the random effect for peer coach cluster k (note that τ_k is multiplied by the intervention indicator Group_{ij} so that the added peer coach correlation is accounted for only amongst intervention participants, as suggest by Roberts et al). Our main goal is to test whether $\beta_1 = 0$ which is the difference in BP change (from baseline to 12 months) between the intervention and control groups.

The main conclusions drawn from this trial will be based on the pre-specified primary hypothesis tested with two-sided p-values at the standard 0.05 level with associated effect size differences and confidence intervals.

MAIN ANALYSIS:

Unadjusted

Secondary: Prespecified variables will include sex, age, and race

All Aim 1 secondary outcomes and Aim 2 intermediate outcomes will be compared between intervention and control participants using the same model above for continuous outcomes and using a logit link for the same model for binary outcomes.

Sensitivity analyses

We will include a sensitivity analysis that will explore whether intervention fidelity influences the effect of the intervention on primary outcomes, treatment receipt (“dose” of intervention: number of visits, phone calls, proportion of required modules delivered). This approach will allow for testing whether greater participation in the intervention was associated with a greater impact on SBP, and if that impact was different for those with different SBP at baseline (include baseline blood pressure in the primary analysis). We will also add a sensitivity analysis among patients enrolled after the COVID pandemic, when all study activities were moved to remote/virtual.

Exploratory Analysis:

1. Restrict sample was restricted to patients who met criteria for uncontrolled hypertension (BP \geq 140/90 mmHg)
2. Pre- vs. During pandemic
 - a. Demographics of Veterans enrolled post-COVID versus pre-COVID – are the Veterans enrolled post-COVID different than Veterans enrolled pre-COVID?
 - b. Separate analysis of primary/secondary outcomes for (1) Veterans with 12 month outcome collected pre-COVID and (2) Veterans with 12 month outcome collected post-COVID – are treatment effects different post-COVID?
3. Secondary analyses to adjust for important baseline covariates in our models. Prespecified variables age, race [others to consider diabetes status because there is a different goal blood pressure for patients with diabetes]

Missing data analyses

If outcome is missing (e.g. exit blood pressure) then will use value in CPRS on the date closest to the exit date (must be +/- 3 months around the date of the exit visit).

- Use outpatient blood pressure as defined by EPRP (EPRP documentation in Teams)

For key analysis variables that have 15% or more missing values, we will analyze patient and clinical factors that are associated with having a missing value. We will then perform analyses using multiple imputations to impute these key variables to allow analysis for all subjects and reduce any bias associated with the missing data. We will perform a sensitivity analysis to determine if missing values have an effect on study outcomes.

Baseline Analysis and descriptive statistics

Equivalence of participants in the intervention and control arms will be assessed on demographic and clinical variables, including outcomes, health status, co-morbidity, and utilization variables. Unadjusted comparisons between intervention groups will be calculated using t-tests and chi-square tests for continuous and categorical outcomes, respectively. Because this is a randomized controlled trial, no systematic bias is anticipated. However, we will conduct adjusted analyses and use as covariates those

factors that are thought *a priori* to be related to the primary and secondary outcomes. We will report summary statistics for all baseline covariates and outcomes (means, standard deviations, and quartiles for continuous variables; frequencies and percentages for categorical variables) by randomized group.

Cost of intervention

We will calculate intervention costs per patient. These costs will include all labor and materials (pamphlets, home blood pressure monitors, etc.) used in the intervention divided by the number of participants.

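### The SAP shows a primary model with baseline SBP and covariates, then labels the main analysis unadjusted, and never reconciles the two

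*SAP*

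**What the plan says.** SAP section 6, under the primary effectiveness heading, commits to a mixed model: "a physician-level and peer health coach random effect will be included in the primary analytic model". The displayed equation has a group term, a baseline term, a covariate term, a provider random effect and a coach random effect that acts only in the intervention arm. Its terms are defined as "Baseline_{ij} is the baseline BP value; x_{ij} are baseline covariates that could affect the outcome". The stated goal is to test whether the group coefficient is zero, and the main conclusions rest on one two-sided test at 0.05.

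Directly below, under *MAIN ANALYSIS*, stands the single word *Unadjusted*, followed by "Secondary: Prespecified variables will include sex, age, and race".

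Four other places in the SAP bear on this:

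- The sensitivity-analysis paragraph of section 6 says, in a parenthesis, "include baseline blood pressure in the primary analysis".
- Item 3 of the exploratory list in section 6 reads "Secondary analyses to adjust for important baseline covariates in our models. Prespecified variables age, race". It leaves diabetes as something to consider and does not mention sex.
- The baseline and descriptive subsection of section 6 links unadjusted comparisons to t-tests and chi-square tests. It then promises adjusted analyses without ranking them: "However, we will conduct adjusted analyses and use as covariates those" factors judged relevant a priori.
- Section 5 gives a longer, open description: "Key covariates include those that have been shown in previous studies to be associated with hypertension control and self-care". It does not connect this set to x.

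Protocol section 5.6 shows the same equation, with x, as the primary model. It carries no *Unadjusted* label.

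**The concern.** A model that contains baseline SBP and x is not unadjusted, so the equation and the label cannot both describe the confirmatory test. Two competent analysts could fit different primary models and each cite the same page of the SAP.

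Three things are at stake. First, if the model is settled after results by arm are known, the 0.05 level is no longer exactly protected. Second, if the label is applied word for word, baseline SBP leaves the model and precision is lost for no saving, because baseline SBP is already measured. Third, the SAP says that secondary and intermediate outcomes "will be compared between intervention and control participants using the same model above for continuous outcomes", with a logit link for binary ones, so they inherit whatever is unclear about the primary model.

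**Working it through.** **1. The texts side by side.** In SAP section 6:

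- Both random effects are in the primary model by an explicit sentence.
- Baseline SBP is in it by the equation and by the parenthesis under sensitivity analyses.
- x is in it by the equation, but outside it by the *Unadjusted* label, the line on secondary variables and exploratory item 3.
- The two lists called prespecified are sex, age and race in one place, and age and race in the other.

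The reading that fits most of this text is the mixed model with group, baseline SBP and both random effects, without x.

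**2. The plan's own sample size.** Protocol section 5.6 gives 5 mmHg, SD 14.2, 80% power, alpha 0.05, ICC 0.015 for providers (cluster size 5), ICC 0.007 for coaches (cluster size 35) and 15% attrition.

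- Without clustering: 2 × (1.96 + 0.842)² × 14.2² / 5² = 127 per arm.
- Design effect, control: 1 + 4 × 0.015 = 1.06. Intervention: 1.06 + 34 × 0.007 = 1.298. Mean: 1.179.
- 127 × 1.179 = 150 per arm, 300 in total, and 300 / 0.85 = 353. The protocol projects 354.

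The figure reproduces. It uses one SD and no variance explained by covariates, so it does not show which model was meant.

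**3. Only x in doubt (the likelier reading).** Suppose x explains a fraction R² of the residual variance. R² is not in the documents; 1 to 5% is assumed. Under the null, the estimators with and without x correlate at √(1 − R²). From the bivariate normal, the chance that at least one |Z| exceeds 1.96 is:

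| R² | correlation | type I error if the smaller p is reported |
|---|---|---|
| 1% | 0.9950 | 5.5% |
| 2% | 0.9899 | 5.7% |
| 5% | 0.9747 | 6.0% |

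Power for 5 mmHg uses 170 per arm (200 × 0.85) and SE = √(Var × (1.06 + 1.298) / 170), where rho is the assumed correlation between baseline and 12-month SBP. The protocol does not say whether 14.2 is the SD of SBP at one visit or of change, so both are shown.

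- One-visit SD, Var = (1 − rho²) × 14.2²: from R² = 0 to 5%, power goes from 88.0 to 89.5% at rho 0.3 and from 98.7 to 99.0% at rho 0.7.
- SD of change, Var = 14.2² × (1 + rho) / 2: from 96.0 to 96.7% at rho 0.3 and from 90.0 to 91.4% at rho 0.7.

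**4. Baseline SBP also dropped (the literal label).** Change without baseline has variance 2(1 − rho) × SD², against (1 − rho²) × SD² with it. The ratio is 2/(1 + rho). The last column is the type I error if the smaller p of these two fits is reported; their estimators correlate at √((1 + rho)/2).

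| rho (assumed) | variance ratio | power without / with baseline, 14.2 as one-visit SD | power without / with baseline, 14.2 as SD of change | type I error |
|---|---|---|---|---|
| 0.3 | 1.54 | 71.5 / 88.0% | 84.8 / 96.0% | 7.8% |
| 0.5 | 1.33 | 84.8 / 93.2% | 84.8 / 93.2% | 7.3% |
| 0.7 | 1.18 | 97.1 / 98.7% | 84.8 / 90.0% | 6.8% |

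Power without baseline falls below the planned 80% only if 14.2 is a one-visit SD and rho is below 0.43. With the 177 per arm that the protocol also states, the threshold is about 0.41.

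**5. The label as a t-test.** A t-test has neither random effect. On the plan's own design effects the variance of the group difference is 1.179 times what a t-test assumes, so the standard error would be too small by a factor of √1.179 = 1.09.

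**The case against.** The strongest reply is that the SAP does answer the question. The label, the line on secondary variables and exploratory item 3 all put covariate adjustment outside the main test, and the parenthesis keeps baseline SBP inside it. What is left is an equation not trimmed to match its label. The plan also commits to one test at 0.05 and to covariates chosen a priori. Most of this stands. It makes the intended model a good guess and keeps the consequences small. It does not remove the contradiction, because the equation is what an analyst would code, and nothing says that x is dropped from it.

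A reader might infer that the covariate set is wide open. The documents do not support that. The SAP names its secondary variables, and the open choice is mainly sex, diabetes, and x in or out. Protocol section 5.6 defines x by pointing to a Section C.6.5 that is not in the protocol's contents list. It may sit in the attached grant application, which is not available here, so the protocol cannot be faulted for leaving x undefined. Protocol section 5.5 does speak of adjusting for differences between the arms, but it first limits the covariates to those supported by earlier studies, and the SAP does not repeat that phrase.

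A reader might also infer that the primary test is a plain t-test with reduced power. The SAP uses *unadjusted* for t-tests only under the baseline and descriptive heading, and the text on the primary model says the opposite.

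**Conclusion.** The contradiction is real and concerns the trial's only confirmatory test, so it should be corrected. Its likely numerical effect is small. With baseline SBP and both random effects kept, no choice about x biases the estimate under randomization, and power moves by about 1.5 points at most. Type I error rises to 5.5 to 6.0% only if both fits are run, the smaller p-value is reported, and x explains an assumed 1 to 5% of residual variance.

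The larger figures (type I error of 6.8 to 7.8%, and power as low as 71.5%) belong to the literal reading, which the rest of the SAP speaks against. They also depend on an assumed rho and on what the SD of 14.2 measures. They show why the label should not be left to be applied as written; they are not a forecast of what the trial will do. Nor do the documents make x in the primary model an error: a fixed, prespecified x would be equally valid.

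**What to change.** Replace the word *Unadjusted* with one sentence, for example: the main test of the group coefficient comes from the mixed model with group, baseline SBP, a provider random effect and an intervention-arm coach random effect, and this is the only primary test.

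Then:

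- State explicitly whether x is in that model, and make the displayed equation match. The SAP's own label and its line on secondary variables indicate that x is out. If so, move x to the secondary adjusted analysis and note the difference from the equation in protocol section 5.6. If x is to stay, list its members.
- Use one fixed covariate list under both the main-analysis and exploratory headings. Sex, age and race is the fuller of the two lists already there. Decide diabetes in or out, and keep to the a priori rule.
- Say that the model for secondary and intermediate outcomes is this same model, with the corresponding baseline value.

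The cost is SAP wording only. Baseline SBP, sex, age and race are already collected. The change should be made before outcomes are examined by arm.
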